1.2 Study Objective

This study aims to disentangle pharmacological from expectation effects and their interaction during discontinuation of antidepressants and explore their underlying processes. More specifically the following questions and hypotheses were stated:

- How do treatment and treatment expectation contribute to discontinuation symptom load? Treatment (discontinuation of AM vs. continuation) and treatment expectation (high vs. medium) interact in modulating discontinuation symptom load among remitted major depressive disorder (MDD) patients over the course of the experimental phase.
- In what way can discontinuation symptom load be affected by treatment expectation, i.e. the placebo-effect, alone? Remitted MDD patients who remain on their antidepressant medication will show a higher discontinuation symptom load with moderate than with high expectation.
- In what way can the discontinuation symptom load be affected by pharmacological factors alone? Remitted MDD patients with moderate treatment expectation will show a higher discontinuation symptom load if antidepressant medication is discontinued versus if antidepressant medication is continued.
- In what way does the discontinuation symptom load differ between high and moderate treatment expectation? Remitted MDD patients who discontinue their antidepressant

medication will show a higher discontinuation symptom load with high than with moderate treatment expectation.

- The relationship between treatment expectation and discontinuation symptom load will vary according to stress ratings, prior side effects of antidepressant medication, prior discontinuation experience, neuroticism, anxiety, somatosensory amplification, and illness framework.

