2.1 Trial Design

PHEA is a prospective, randomised, parallel-group, partly blinded, open-hidden discontinuation trial with a 2x2-factorial design. The allocation ratio is 1:1:1:1 for the four groups:

- Treatment discontinuation and high expectation - open discontinuation (OD):
Patients in this group receive gradually decreasing doses of prescribed AM in encapsulated tablets and will receive full information about their treatment (i.e., high expectation).
- Treatment continuation and high expectation - open continuation (OC):
Patients in this group remain on prescribed AM in identical encapsulated tablets and will receive full information about their treatment (i.e., high expectation).
- Treatment discontinuation and medium expectation - hidden discontinuation (HD):
Patients in this group will receive gradually decreasing doses of prescribed AM in encapsulated tablets and will be informed about a 50% chance of discontinuing versus remaining on AM (i.e., moderate expectation).
- Treatment continuation and medium expectation - hidden continuation (HC):
Patients in this group will remain on prescribed AM in identical encapsulated tablets and will be informed about a 50% chance of discontinuing versus remaining on AM (i.e., moderate expectation).

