2.3 Sample Size

A medium effect size of $f=0.22$, a significance level of $\alpha=0.05$, and a power of 80% were assumed. This resulted in 168 patients needed in total (i.e. 42 per group) using an ANOVA model (with main effects and interactions). Furthermore, with an expected drop-out rate of at most 15%, in total 196 patients need to be recruited (i.e. 49 per group).

Sample size calculation was conducted using G*Power (version 3.1.9.2).

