3.1 Confidence Intervals and *P* Values

All applicable statistical tests will be two-sided and will be performed using a 5% significance level. All confidence intervals presented will be 95% and two-sided. Analyses of secondary and safety outcomes will be performed exploratory without adjustment for multiple testing.

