5.3.2 Analysis of Secondary Endpoints

Continuous outcomes

Linear models (ANCOVA) will be used with the following variables:

- Dependent variables:
 - AUC value based on DESS scores week 14 till week 52, i.e., assessed at FU1-FU3
 - Change from baseline (t1) of patient-reported stress scores based on PSS-10 scores at t9 (12 weeks after t1)

- Change from baseline (t1) of patient-reported state-anxiety scores based on STADI scores at t9 (12 weeks after t1)
- Independent variables:
 - Random group as two factors (i.e. 1st factor: treatment discontinuation vs continuation; 2nd factor; high vs. medium expectation) and their interaction
 - The stratification variables of the randomization process:
 - *intake duration with 24 months as a marker for long-term intake (<24 months of AM vs. >24 months)*
 - *risk of developing discontinuation symptoms associated with the antidepressant medication (moderate vs. higher or unknown risk)*
 - Concerning secondary endpoint a), the corresponding pseudo baseline value (t1) will additionally be included as covariate.

Primary interest lies in the interaction between the two factors describing the random group. The post-hoc comparisons between the subgroups will be addressed exploratively. If the corresponding p-value (for the interaction) is >0.15 the model will be calculated without the interaction and the independent main effects of the 2 factors will be assessed.

Normal distribution of the residuals will be checked graphically via a histogram of residuals. If the assumption of normally distributed residuals is clearly violated, a sensitivity analysis using the log-transformation for the dependent variable will be performed to judge the robustness of the results. Adjusted mean values and adjusted effect estimators (mean differences) with corresponding 95%-Wald confidence intervals and p-values will be given.

The ICC (intra-class correlation) will also be reported, where appropriate.

Linear mixed model (random intercept model) will be used with the following variables:

- Dependent variable:
 - Bias score (emotional versus neutral faces, measured in ms)
- Independent variables (fixed factors):
 - Expectation concerning recurrence of discontinuation symptoms derived from the factors of the random group: high expectation (open discontinuation group) versus moderate expectation (both hidden groups, continuation and discontinuation) versus low expectation (open continuation group)

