 - Type of emotion (happy versus sad versus fearful)
 - 3x3 interaction of expectation and emotion
 - The stratification variables of the randomization process:
 - *intake duration with 24 months as a marker for long-term intake (<24 months of AM vs. >24 months)*
 - *risk of developing discontinuation symptoms associated with the antidepressant medication (moderate vs. higher or unknown risk)*
- Variable used as random effect (intercept)
 - Patient ID

Primary interest lies in the interaction between expectation and emotion. The post-hoc comparisons between the expectation - subgroups regarding the different emotions will be addressed exploratively. If the corresponding p-value (for the interaction) is >0.15 (i.e. the expectation groups do not differ substantially regarding the different emotions) the model will be calculated without the interaction

and the independent main effects of the 2 factors will be assessed (again with post-hoc comparisons if appropriate).

Adjusted mean values and adjusted effect estimators (mean differences) with corresponding 95%-Wald confidence intervals and p-values will be given.

The ICC (intra-class correlation) will also be reported, where appropriate.

Binary outcome

Binary logistic model will be used with the following variables:

- Dependent variable:
 - Binary variable judging any recurrence of depression during 13 week experimental period (i.e. yes/no) at t9
- Independent variables:
 - Random group as two factors (i.e. 1st factor: treatment discontinuation vs continuation; 2nd factor; high vs. medium expectation) and their interaction
 - The stratification variables of the randomization process:
 - *intake duration with 24 months as a marker for long-term intake (<24 months of AM vs. >24 months),*
 - *risk of developing discontinuation symptoms associated with the antidepressant medication (moderate vs. higher or unknown risk)*

Primary interest lies in the interaction between the two factors describing the random group. The post-hoc comparisons between the subgroups will be addressed exploratively.

Again, a model without the interaction term of the random group-factors but only the 2 main factors is calculated if the corresponding interaction p-value is above 0.15.

Rates and adjusted effect estimators (odds ratios) with corresponding 95%-Wald confidence intervals and p-values will be given.

Time-to-event outcome

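### The bias-score mixed model merges the four randomised groups into three expectation levels with no discontinuation term, so its expectation main effect and by-emotion contrasts mix expectation with drug effects

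*SAP*

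**What the plan says.** Section 2.1 defines a 2x2 factorial trial with 1:1:1:1 allocation to open discontinuation (OD), open continuation (OC), hidden discontinuation (HD) and hidden continuation (HC). The two hidden groups get the same 50% instruction and differ only in drug: "Treatment discontinuation and medium expectation - hidden discontinuation (HD" and "Treatment continuation and medium expectation - hidden continuation (HC".

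The ANCOVA, logistic and Cox models in sections 5.3.1 and 5.3.2 all enter both randomised factors and their interaction. The mixed model for the bias scores does not. Its group term is "high expectation (open discontinuation group) versus moderate expectation (both hidden groups, continuation and discontinuation) versus low expectation (open continuation group". The other terms are type of emotion, expectation by emotion, the two stratification variables and a random patient intercept.

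Primary interest is in the expectation-by-emotion interaction. Two further sets of results are promised. On the contrasts within emotions: "The post-hoc comparisons between the expectation - subgroups regarding the different emotions will be addressed exploratively". If the interaction p-value exceeds 0.15, the interaction is dropped "and the independent main effects of the 2 factors will be assessed (again with post-hoc comparisons if appropriate". Adjusted mean differences, 95% confidence intervals and p-values will be given.

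**The concern.** Section 1.2 states the purpose: "This study aims to disentangle pharmacological from expectation effects and their interaction during discontinuation of antidepressants". Its directional hypotheses, written for symptom load, each hold one factor fixed: HC vs OC, HD vs HC, and OD vs HD. The three-level model can return none of these comparisons for the bias scores.

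Moving from low to high expectation on this scale also moves from nobody discontinuing to everybody discontinuing. If stopping an antidepressant itself changes attention to emotional faces, the model will report that change as an expectation effect, with a p-value and a confidence interval. The one comparison that isolates the drug at equal instruction, HD vs HC, disappears into the pooled middle level. Sections 5.2 and 5.4 name no drug-adjusted sensitivity model for this endpoint, and the SAP does not assume that the drug leaves bias scores unchanged.

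**Working it through.** **The plan's own figure.** The SAP states no calculation for the bias-score model. The group size comes from section 2.3: "A medium effect size of $f=0.22$, a significance level of $\alpha=0.05$, and a power of 80% were assumed". With a noncentral F test, 1 numerator df, four groups and noncentrality N x 0.22², the smallest N is 165. Equal groups need 168, or 42 per group (power 0.809), which reproduces the SAP. The two-sided 5% level is from section 3.1.

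**Algebra, with no outside figure.** Let the drug effect be δ and the expectation effect zero. The cell means are OD = δ, HD = δ, HC = 0, OC = 0. The pooled moderate mean is (δ + 0)/2 = δ/2. Then:

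- high - low = δ - 0 = δ
- high - moderate = δ - δ/2 = δ/2
- moderate - low = δ/2 - 0 = δ/2

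With a drug term added, the design has rank 4 on four cells and is estimable, because the hidden groups contain both drug states. All three expectation contrasts then become 0.

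**Size, as illustration only.** Assumptions: 42 per group, SD 1 for each of three bias scores, within-patient correlation 0.5, no expectation effect, δ equal across emotions, strata ignored. The SD of a patient's mean over three emotions is sqrt((1 + 2 x 0.5)/3) = 0.816. The tests have 168 - 3 = 165 error df. Noncentralities for the averaged contrasts:

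- OD vs OC: δ/(0.816 x sqrt(2/42)) = δ/0.178
- adjacent levels: (δ/2)/(0.816 x sqrt(1/42 + 1/84)) = (δ/2)/0.154
- 2-df main effect: 84 x (δ/2)²/0.667

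For a single emotion the standard errors are 0.218 and 0.189. False rejection rates in per cent, against a nominal 5:

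| Test | δ = 0.2 | 0.3 | 0.4 | 0.5 |
|---|---|---|---|---|
| OD vs OC, averaged over emotions | 20.0 | 38.8 | 60.7 | 79.7 |
| Adjacent levels, averaged | 9.9 | 16.2 | 25.2 | 36.4 |
| 2-df expectation main effect | 15.4 | 30.1 | 49.9 | 70.2 |
| OD vs OC, one emotion | 14.9 | 27.7 | 44.5 | 62.5 |
| Adjacent levels, one emotion | 8.2 | 12.4 | 18.3 | 26.0 |

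A split-plot simulation (3,000 runs per scenario) gives 20/37/59/78% for the first row. Its range over δ is 24% to 87% at correlation 0.3 and 18% to 71% at 0.7. Counting only trials that also have interaction p > 0.15, it gives 17/31/49/67%. With no drug effect, all tests reject in about 5%.

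**The interaction test.** With δ equal across emotions, the expectation-by-emotion test rejects in 3.9% to 5.6% of simulated trials, which is nominal. If the drug acts on one emotion only (correlation 0.5), it rejects in 10/19/34/53%.

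**The case against.** The case for leaving the model alone has five parts.

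- *The stated target is largely spared.* The interaction test keeps its level unless the drug effect differs by emotion. This is correct and limits the point to the main effect and the by-emotion contrasts.
- *The endpoint is exploratory* (sections 2.4 and 3.1). This lowers the priority and excuses the lack of multiplicity adjustment. It does not excuse bias: the contrast measures a mixture, and more data would not change that.
- *The sizes are hypothetical, and OD vs OC is the worst case.* Both are true. The adjacent-level and 2-df rates are tabulated for that reason. The percentages show what would follow from a drug effect, not that one exists.
- *The coding is deliberate and open.* The factor is meant as expected symptom recurrence, a different construct from the open/hidden factor elsewhere, and section 5.3 shows HD and HC separately in descriptive tables. Those tables do not correct the modelled estimates, and the shared instruction is exactly why HD vs HC is informative.
- *A caveat would be cheaper.* Stating that the contrasts combine both effects would make the report honest, but it would still not separate them.

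**Conclusion.** The point holds. That the high-low contrast carries the full drug effect and each adjacent contrast half follows from the group definitions and the model terms alone. How often this would mislead depends on assumed values. For a drug effect of 0.2 to 0.5 SD equal across emotions, with 42 per group and correlation 0.5, the averaged OD vs OC contrast would be falsely significant in about 20% to 80% of trials, and the same contrast within one emotion in about 15% to 63%. The interaction test is affected only if the drug effect varies by emotion. The primary analysis, the sample size and the other secondary models are untouched. The sponsor should change this model, though it is a matter for an exploratory endpoint.

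**What to change.** Fit the four randomised groups crossed with emotion. This is the same as the two randomised factors and their interaction, each crossed with emotion. Keep the strata and the random intercept. Report, overall and by emotion:

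- HD vs HC as the drug effect at equal instructed expectation;
- OD vs HD and HC vs OC as expectation contrasts at fixed drug status.

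Do not let the p > 0.15 rule remove the treatment by open/hidden interaction in this model. On this scale the open groups hold both the highest and the lowest expectation. With drug effect P and equal expectation steps totalling E, the means are OD = P + E, HD = P + E/2, HC = E/2, OC = 0. The open and hidden averages are then both (P + E)/2, so the open/hidden main effect is zero and the expectation effect sits wholly in the interaction.

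If one drug-adjusted high-low contrast is also reported, state that it equals (OD - OC) - (HD - HC), which is E above. It is a pure expectation effect only if the drug effect is the same in the open and hidden groups.

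The change uses data already held. The cost is precision:

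| Contrast | One emotion (SE in SD) | Mean of three, correlation 0.5 |
|---|---|---|
| High-moderate, pooled (current) | sqrt(1/42 + 1/84) = 0.189 | 0.154 |
| OD vs HD (proposed) | sqrt(2/42) = 0.218 | 0.178 |
| High-low, unadjusted (current) | sqrt(2/42) = 0.218 | 0.178 |
| High-low, drug-adjusted | sqrt(4/42) = 0.309 | 0.252 |

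The group-by-emotion test goes from 4 to 6 df. If the three-level model is kept as well, label its contrasts as combined expectation and drug effects.

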2.6 Timing of Outcome Assessments

See Table 1.

Table 1. Schedule of enrolment, intervention and assessments according to SPIRIT-PRO.

	STUDY PERIOD								
	Enrolment		Allocation	Experimental phase			Clinical observation		
Timepoint	S1	S2	t0	t1-t5	t6-t8	T9	FU1	FU2	FU3
Weeks	-2	-1	0	1/2/3/4/5	7/9/11	13	26	39	52
Enrolment									
Eligibility screen	✓	✓							
Informed consent			✓						
Initial consultation prescribing physician			✓						
Randomization				✓					
Interventions					✓	✓	✓		

Discontinuation versus continuation of AM High versus moderate expectation (open versus hidden treatment)			✓ ✓	✓ ✓	✓ ✓	
Assessment						
Primary outcome measures						
Discontinuation symptom load (DESS)		✓	✓	✓	✓	
Secondary outcome measures						
Discontinuation symptom load (DESS)					✓	✓
Recurrence			✓	✓	✓	✓
Psychophysiological stress (PSS-10)*		✓			✓	
State anxiety (STADI State)*		✓			✓	
Attentional, affective processing (Posner task)*					✓	
Possible modulators						
Psychophysiological stress (PSS-10)*		✓				
Side effects of antidepressant medication (GASE*)		✓			✓	
Prior discontinuation experience (GEEE _{PRE} *)		✓				
Personality traits (BFI-10)*		✓				
Trait anxiety (STADI State)*		✓				
Somatosensory amplification (SSAS)*		✓				
Illness perception (single item)		✓				
Further assessments						
Optional: rsfMRI		✓	✓ (t1)			
AM blood serum level			✓(t1)		✓	
Trait marker stress*		✓				
Adherence (single item)		✓	✓	✓	✓	✓
Self-reported depressive symptoms (BDI-II)*	✓	✓	✓	✓	✓	✓
Expert-rated depressive symptoms (MADRS)*	✓	✓	✓	✓	✓	✓
Prior discontinuation symptoms (DESS _{PAST})		✓				
Current treatment effects (GEEE _{ACT} *)		✓	✓	✓	✓	✓
Expectations (TEX-Q*)		✓	✓	✓	✓	✓
Expectations (GEEE _{EXP} *)		✓	✓	✓	✓	✓
Behavioral inhibition/approach (BIS-BAS scale)*		✓				
Psychopathology (SCID-5-CV interview)*	✓					
Well-being (SWEMWBS)		✓	✓	✓	✓	✓
Depression and Anxiety (PHQ-4)					✓	✓
Subjective Impairment (PDI*)		✓	✓(t1,t5)		✓	
Substance Use & Coping			✓(t1,t5)	✓(t7)	✓	
Screener Warmth & Competence*		✓	✓(t5)		✓	
Adverse events (single safety items)		✓	✓	✓	✓	✓
Suspicions about treatment (GEEE _{END})*					✓	
Demographic* & medical characteristics		✓			✓	✓
Debriefing & close-out						
Debriefing					✓	
Consultation prescribing physician					✓	
Individualized discontinuation plan for continuation groups						✓

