4.1 Screening Data

Available screening data include:

- Age
- Gender
- Single vs. recurrent depressive episodes

These will be reported.

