5.1.2 Secondary endpoints

- a) Discontinuation symptom load over the clinical observation period (i.e. assessments from FU1 till FU3 will be considered and cover reported symptoms between week 14 until week 52) assessed by the Discontinuation Emergent Signs and Symptoms Scale (DESS; Rosenbaum et al., 1998):
As for the primary endpoint AUC will be calculated from the measurements of FU1, FU2, and FU3.
- b) Recurrence (yes / no) during experimental phase, i.e., appearance of a new depressive episode after full, sustained remission of depressive symptoms over the experimental period (i.e., assessments from t1 till t9 will be considered and cover reported symptoms between week 1 until week 13). Recurrence will be monitored weekly during run-in and (dis-)continuation phase and biweekly during monitoring phase, based on Beck Depression Inventory II and Montgomery Asberg Depression Rating Scale scores (BDI-II, Hautzinger et al., 2009; Montgomery-Asberg Depression Rating Scale [MADRS+], (Davidson et al., 1986; Schmidtke et al., 1988; Williams & Kobak, 2008). If recurrence is suspected (as indicated by BDI-II score >19 or MADRS score >21 over two study visits), corresponding SCID-5-CV sections will be conducted to (dis-)confirm recurrence (Beesdo-Baum et al., 2018; First et al., 2016).

Binary variable first recurrence of depression during experimental phase of trial (i.e. yes/no) will be given at t9.

- c) First recurrence over the course of the trial, i.e., appearance of a new depressive episode after full, sustained remission of depressive symptoms will be monitored weekly during run-in and (dis-)continuation phase, biweekly during monitoring phase, and at 26, 39, and 52 weeks post-baseline, as determined in a time-to-event analysis. Assessments from t1 till FU3 will be considered and cover reported symptoms between week 1 until week 52 based on Beck Depression Inventory II and Montgomery Asberg Depression Rating Scale scores (BDI-II, Hautzinger et al., 2009; Montgomery-Asberg Depression Rating Scale [MADRS+], (Davidson et al., 1986; Schmidtke et al., 1988; Williams & Kobak, 2008). If recurrence is suspected (as indicated by BDI-II score >19 or MADRS score >21 over two study visits), corresponding SCID-5-CV sections will be conducted to (dis-)confirm recurrence (Beesdo-Baum et al., 2018; First et al., 2016). Calendar week of start of new depressive episode will be examined and recorded.

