A Cox proportional hazards model will be used for the endpoint first recurrence over the course of the clinical trial. Independent variables are:

- Random group as two factors (i.e. 1st factor: treatment discontinuation vs continuation; 2nd factor; high vs. medium expectation) and their interaction
- The stratification variables:
 - intake duration with 24 months as a marker for long-term intake (<24 months of AM vs. >24 months),
 - risk of developing discontinuation symptoms associated with the antidepressant medication (moderate vs. higher or unknown risk)

Primary interest lies in the interaction between the two factors describing the random group. The post-hoc comparisons between the subgroups will be addressed exploratively.

If the corresponding p-value (for the interaction) is >0.15 the model will be calculated without the interaction and the independent main effects of the 2 factors will be assessed.

The proportional hazards assumption will be checked graphically via Schoenfeld residuals.

Event rates and adjusted effect estimators (hazard ratios) with corresponding 95%-Wald confidence intervals and p-values will be given.

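### The Cox model for first recurrence to week 52 leaves out the depression score collected before randomisation: a valid analysis, but possibly a less efficient one

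*SAP*

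**What the plan says.** In SAP section 5.3.2, under the time-to-event outcome, the plan states: "A Cox proportional hazards model will be used for the endpoint first recurrence over the course of the clinical trial". The list of independent variables opens with "Random group as two factors (i.e. 1st factor: treatment discontinuation vs continuation; 2nd factor; high vs. medium expectation) and their interaction". The other two entries are the randomisation strata: the first is given as "intake duration with 24 months as a marker for long-term intake (<24 months of AM vs. >24 months", and the second is the discontinuation-symptom risk attached to the drug. That makes five model terms. None is a measure of depression, and section 5.4 (Sensitivity Analyses) plans no analysis that adds one.

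Section 5.1.2 c) describes how a recurrence is established: "If recurrence is suspected (as indicated by BDI-II score >19 or MADRS score >21 over two study visits), corresponding SCID-5-CV sections will be conducted", and the interview then confirms or rejects it. In Table 1 (section 2.6) the rows "Self-reported depressive symptoms (BDI-II" and "Expert-rated depressive symptoms (MADRS" carry ticks from the enrolment columns on. The table layout is damaged in the available text, so individual ticks cannot all be placed. Section 2.7 puts t9 (week 13) 13 weeks after randomisation, so randomisation falls at week 0 and the screening visits precede it. Section 4.1 also lists "Single vs. recurrent depressive episodes" among the screening data.

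Elsewhere the plan does use a baseline value: the DESS score at t1 is a covariate for the primary endpoint (5.3.1) and for secondary endpoint a) (5.3.2).

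**The concern.** A patient who enters with more residual symptoms may well be closer to a recurrence than one who enters with none, and the scales that measure those symptoms also open the way to the recurrence diagnosis. If the score is prognostic, leaving it out of a Cox model lowers power even under perfect randomisation and moves the estimated hazard ratio towards 1. It also leaves any chance imbalance between four arms of 49 unadjusted. Section 5.3.2 names the interaction as the effect of main interest and removes it when its p-value exceeds 0.15, so lost precision bears on that decision too. The data are already scheduled, so the question is only whether the model should use them.

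**Working it through.** **1. Figures in the plan.** The SAP states no power, event count or hazard ratio for recurrence. Its only sample-size figure (section 2.3) concerns an ANOVA: f = 0.22, α = 0.05, power 80%. For a 1-df effect in four groups, with noncentrality N × f² and N − 4 error degrees of freedom, the smallest N is 165 (power 80.2%). Rounded up to equal groups this is 168 (80.9%), as stated. For 15% drop-out, 165 / 0.85 = 194.1, so 195, or 196 in equal groups, as stated. (Starting from 168 gives 198, a trivial difference.) The 196 recruited patients are used below.

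**2. Assumptions not in the documents.**
- 15%, 30% or 45% of patients have a recurrence by week 52.
- The standardised baseline score has a hazard ratio of 1.0, 1.25, 1.5 or 2.0 per SD.
- The hazard is constant, 15% of patients are censored early at a uniform time, and the strata have no effect of their own.

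**3. Effect size in each scenario.** It was set to 80% power by the Schoenfeld formula with D = event rate × 196 events. With (1.96 + 0.84) = 2.80:
- Main effect: log HR = 2.80 × 2 / √D. For D = 58.8 this is 0.73, HR 2.08. For D = 29.4 and 88.2 the HRs are 2.81 and 1.82.
- Interaction: log of the ratio of HRs = 2.80 × 4 / √D, giving ratios of 7.90, 4.31 and 3.30 at 15%, 30% and 45% events.

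**4. Simulation.** There were 3,000 trials per setting, with two-sided 5% Wald tests. Both models adjust for the two strata; one adds the score. Power in %, without → with the score:

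| Effect | Events | HR 1.25 per SD | HR 1.5 per SD | HR 2.0 per SD |
|---|---|---|---|---|
| Main | 15% | 73.9 → 74.0 | 73.9 → 74.9 | 72.7 → 75.9 |
| Main | 30% | 77.1 → 77.5 | 76.9 → 78.2 | 70.1 → 77.8 |
| Main | 45% | 77.3 → 78.4 | 75.1 → 77.8 | 68.4 → 78.6 |
| Interaction | 15% | 69.1 → 69.7 | 71.2 → 72.1 | 68.3 → 71.7 |
| Interaction | 30% | 76.8 → 77.7 | 76.6 → 78.8 | 70.6 → 77.6 |
| Interaction | 45% | 77.0 → 78.6 | 76.2 → 80.0 | 66.0 → 78.0 |

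The gains are 0.1-1.6 points (weak), about 1-4 (moderate) and 3-12 (strong). With no prognostic value (HR 1.0) the two models differ by less than 0.5 points in either direction. The simulation error of one power figure is about √(0.77 × 0.23 / 3000) = 0.8 points. Both models are fitted to the same data, so their difference is steadier than that.

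**5. Type I error** (30% events, HR 2.0 per SD): main effect 4.6% without and 5.1% with the score; interaction 5.1% and 5.3%.

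**6. Hazard ratio** (main effect, 45% events, HR 2.0 per SD, value simulated 1.82): median estimate 1.71 without and 1.83 with the score.

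**7. Room in the model.** One score takes five terms to six; episode history would make seven. At 15% events there are 29.4 events, or 5.9, 4.9 and 4.2 per term. At 30% there are 58.8, or 11.8, 9.8 and 8.4.

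**The case against.** The strongest reply is that nothing here is wrong. Adjusting for the randomisation strata is a valid, fully specified analysis. Section 2.4 makes the endpoint exploratory, and no powered claim depends on it. That stands: this is a missed efficiency gain, not an error.

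Second, section 4.2 admits only fully remitted patients, with remission of at least four months or two years depending on history. This probably narrows the spread of baseline scores and makes the weak or moderate columns the likelier ones. It does not remove the spread, because the SAP states no BDI-II or MADRS ceiling at entry.

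Third, section 5.2 censors at treatment switching, which the simulation does not model. Switching would reduce the number of events, and the gain is smallest when events are few.

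Several stronger readings are tempting but not supported:
- *Crossing the threshold is the event.* A score above it over two visits only prompts the SCID-5-CV, which may reject recurrence.
- *The planned hazard ratio is biased.* The drift towards 1 is mostly non-collapsibility: the two models estimate differently conditioned hazard ratios.
- *Both strata were picked for discontinuation symptoms.* Section 2.2 says so of the drug-risk stratum only; it calls intake duration a marker for long-term intake.
- *Recurrence is singled out.* The models for endpoints b), d), e) and f) list no separate baseline covariate either, and the t1 adjustment elsewhere uses the same scale as the outcome, which a recurrence endpoint cannot do.

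**Conclusion.** The point holds as a minor improvement. The model omits a pre-randomisation score on the very scales that gate the diagnosis, and including it costs almost nothing. A gain of 0-4 power points is plausible for a weak or moderate predictor. A gain of 7 points or more appears only when the score predicts strongly (HR 2.0 per SD) and at least 30% of patients have a recurrence. These figures depend on event rates and prognostic strengths that the SAP does not give. A reader might infer that power is certainly being thrown away, or that the trial's main conclusion is at risk. Neither follows: with a score of no prognostic value the gain is nil, the type I error is near 5% either way, and the primary endpoint is untouched.

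**What to change.** Before unblinding, add one named score to the independent variables of the Cox model for endpoint c) in section 5.3.2, for example the last BDI-II total before randomisation, as a continuous term. Name both the scale and the visit, because the two scales are correlated and leaving either choice open invites a data-driven one. Take a value from before randomisation; t1 comes after it. Keep both strata, and report the strata-only model alongside.

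Do not add single versus recurrent MDD, and do not extend the adjustment to endpoint b), unless the event count supports it.

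The cost is SAP wording, one more model term, and a hazard ratio that is conditional on the score. No new data are needed.
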